17.2 On-site Monitoring

Monitoring will be carried out as required following a risk assessment and as documented in the SPECIAL Quality Management Plan. Additional on-site monitoring visits may be triggered, for example by poor CRF return, poor data quality, excessive number of patient withdrawals or deviations. If a monitoring visit is required the Trial Office will contact the site to arrange a date for the proposed visit and will provide the site with written confirmation. Investigators will allow the SPECIAL trial staff access to source documents as requested.

17.3 Central Monitoring

Where patients and carers have given explicit consent sites are requested to send in copies of signed Informed Consent Forms for in-house review.

Trials staff will be in regular contact with the site research team to check on progress and address any queries that they may have. Trials staff will check incoming CRF for compliance with the protocol, data consistency, missing data and timing. Sites will be sent Data Clarification Forms requesting missing data or clarification of inconsistencies or discrepancies.

Sites may be suspended from further recruitment in the event of serious and persistent non-compliance with the protocol and/or GCP, and/or poor recruitment. Any major problems identified during monitoring may be reported to the Trial Management Group (TMG) and the relevant regulatory bodies. This includes reporting serious breaches of GCP and/or the trial protocol to the REC.

17.4 Audit and Inspection

The investigator will permit trial-related monitoring, audits, ethical review, and regulatory inspection(s) at their site, providing direct access to source data/documents.

Sites are also requested to notify the Trial Office of any audits or inspections.

17.5 Notification of Serious Breaches

The sponsor of the trial is responsible for notifying the REC in writing of any serious breach of:

- The conditions and principles of GCP in connection with that trial, or
- The protocol relating to that trial, within seven days of becoming aware of that breach.

For the purposes of this regulation, a "serious breach" is a breach which is likely to effect to a significant degree:

- The safety or physical or mental integrity of the subjects of the trial, or
- The scientific value of the trial,

Sites are therefore requested to notify the Trial Office of a suspected trial-related serious breach of GCP and/or the trial protocol. Where the Trial Office is investigating whether or not a serious breach has occurred sites are also requested to cooperate with the Trial Office in providing sufficient information to report the breach to REC where required and in undertaking any corrective and/or preventive action.

18 END OF TRIAL DEFINITION

The end of the trial will be approximately six months after the final patient's last visit. The Trial Office will notify the REC that the trial has ended and a summary of the clinical trial report will be provided within 12 months of the end of trial.

19 STATISTICAL CONSIDERATIONS

19.1 Feasibility Study

In the feasibility study no one outcome is considered primary. The feasibility of proceeding to an RCT shall be assessed through analysis of the criteria listed below. No formal stopping guidelines are proposed. The DMC shall advise the feasibility of proceeding to an RCT based on a review of all feasibility study data, with particular focus on recruitment.

19.1.1 Criteria for progression to Randomised Controlled Trial

The following targets are the key outcomes that will guide the decision to proceed to the RCT (discretion will be used and all outcomes will be viewed as a whole).

- Patients willing to be randomised
- Completion of baseline GHSS (90% of patients)
- Completion of GHSS at three month endpoint (80% of surviving patients)
- Completion of EQ-5D-5L at the six month end point (80% of surviving patients)

19.1.2 Definition of Outcome Measures

19.1.2.1 Patient pathway

- the number of screened and eligible patients identified
- o the number of patients subsequently willing to be registered into the feasibility study
- o the number of patients who find randomisation acceptable

Time to specialist palliative care, defined as the time spent on standard of care will be measured from the date of registration to:

- o The date of referral to SPC
- o The date of first visit for SPC
- Types of treatments given, eliciting
 - differences between standard and early palliative care
 - treatment resulting from SPARC and standard assessments (informing RCT subrandomisation)
- Dose of chemo/radiotherapy received
- Treatment intent (palliative or other)

19.1.2.2 Questionnaire booklet completion

The following will be assessed for each questionnaire (each visit):

- Extent of missing data reported as the proportion of unanswered questions for each questionnaire
- The number of unreturned booklets
- o Overall time taken to complete questionnaire booklet
- o Patient opinion of:
 - number of questionnaires (classified as: too few, just right or too many)
 - appropriateness of each questionnaire/question

19.1.2.3 Overall survival

Overall survival is defined as the time from registration to death (due to any cause) or to date last known to be alive for those not known to have died.

19.1.3 Analysis of Outcome Measures

Full details will be specified in a Statistical Analysis Plan but an outline of the planned analyses is provided below.

Of the outcome measures assessed in the feasibility study some are qualitative and as such statistical analyses are not necessarily applicable. For quantitative measures the data will be reported through descriptive summary statistics and no hypothesis testing will be performed. Where appropriate, measures will be analysed by socio-economic status (English Indices of Deprivation 2010^[18], Scottish Index of Multiple Deprivation 2012^[19]).

Patient Pathway:

- For each participating site the number of eligible patients will be reported as a percentage of those screened, and the number of patients registered will be reported as a percentage of those eligible;
- The expected monthly recruitment rate for the RCT will be reported for each (potential) participating site and overall;
- A prediction of the consent rate will be calculated as the number of patients who are willing to be randomised out of the total number found to be eligible;
- Time to specialist palliative care referral, and to first treatment will be reported via the method of Kaplan and Meier, with median time to specialist palliative care (95% Confidence Interval (CI));
- A listing of the palliative measures defined above will be reported by site and sub-randomisation (standard assessment and SPARC). The details provided by the three participating sites will be compared to the information canvassed form the other sites.

Quality of life questionnaire completion:

The following measures will be reported by questionnaire and visit number, and will be compared to the results of a large Phase III late-stage lung cancer trial^[20]. Where appropriate, measures will be assessed by patient and carer subgroups.

- The mean (standard deviation (sd)) proportion of unanswered questions for each questionnaire
- The number of booklets returned as a percentage of those expected
- The mean (sd) time taken to complete questionnaires

Page | 30 of 64 Version 1.0a, 8 Apr 2016

 The percentage of patients reporting the quantity of questionnaires to be: too few; just right; too many

The patient interviews will be reviewed and discussed to identify any questions and/or questionnaires deemed inappropriate.

To aid reporting in the RCT the treatments observed in the feasibility study will be used to define a 'drop-down list' and implemented on the trial database.

Overall survival:

A Kaplan Meier plot of overall survival will be reported. The six-month survival rate (95% CI) will be reported and the validity of the power calculation for the RCT will be assessed.

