2.2 Outcome Measures

2.2.1 Feasibility Outcome Measures

- The number of potentially eligible patients, the proportion consenting to registration and the proportion willing to be randomised.
 - Questionnaires collecting data on the number of eligible patients seen will be sent to potential recruiting centres
- Patient pathway planning and scoping for Randomised Controlled Trial (RCT) adaptation.
 - Time to specialist palliation, and the treatments delivered (including dose, where applicable) with intent (palliative or not) delivered will be recorded, and aid in defining the primary research question in the RCT.
 - Health service usage; impact on NHS.
- Feasibility of using quality of life (QoL) and resource use questionnaires.
 - Measured by return and completeness rates.
 - Patient opinion on the number of questionnaires and the time taken to complete will be recorded and used to select the best combination of questionnaires.
- To inform design for large scale RCT.
 - Overall survival will be assessed to validate the final sample size calculation for the RCT

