3.2 Randomised Controlled Trial

Stage two will be a non-blinded, prospective randomised controlled interventional trial in which consenting patients with newly diagnosed stage IV NSCLC will be randomly allocated to either standard oncological/respiratory care alone, where the patient could be later referred to palliative care specialists, or early referral to local palliative care services (i.e. within two to four weeks of diagnosis) as well as local standard oncology/respiratory medical treatment and follow-up.

Patients randomised to the early SPC referral arm will be further randomised into two groups where half the patients will be asked to complete a SPARC questionnaire to assess their wider holistic needs.

Patients will be entered into the trial over a three year period and will be followed up for three years or until death.

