7 ASSESSMENTS AND DELIVERY OF INTERVENTION

SPC will be delivered variably according to local service configuration. In some sites the service will be run within the NHS; in others it will be supplied from a local independent charitable hospice service. In essence, all SPC services are supplied by a combination of specialists trained in palliative medicine and nursing, and other clinical and allied health professionals who may have varying degrees of specialisation. Both stages of the study will describe and characterise which elements of these are applied, in what order and to what degree.

Sites in which all patients are referred early, i.e. within two to four weeks, to SPC will not be eligible to participate in this trial. In addition, in order to be able to participate as a site in the RCT trial, the SPC input should be offered by a palliative medicine doctor and nurse.

Health technologies which are used during the process of cancer care and symptom management for trial patients will also captured in both stages of the trial. These include:

- · Radiotherapy including date of last dose in relation to time of death
- Cytotoxic chemotherapy including date of last dose in relation to time of death
- Targeted biological therapy including date of last dose in relation to time of death
- Other interventional health technologies (see Appendix 1 for details)
- Use of interventions around the end of life (see Appendix 1 for details)

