19.2.5.1 Global Health Status Score

Assuming a median survival time in these patients of six months and an exponential distribution, it is expected that 70% of randomised patients will be alive at three months. Experience in the BTOG2 trial shows that we would expect high compliance in these remaining patients, so we assume a further 5% dropout for reasons other than death, giving a total loss of 35% of randomised patients. From literature, GHSS in patients with metastatic NSCLC is 58.8 with standard deviation of 23 points and data from the stage IV patients in the BTOG2 trial shows similar values with a mean GHSS at baseline of 61.5 and standard deviation (SD) of 23. A difference of seven points between treatment groups at three months, which is a standardised effect size of 0.3, is considered to be realistic and clinically relevant. Assuming a 5% two-sided significance level and 80% power the analysis requires a total of 342 patients to detect this level of difference and thus 525 randomised patients. For 90% power the analysis requires a total of 456 patients and thus 700 randomised patients.

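### Feasibility study: Kaplan-Meier for time to specialist palliative care overstates referral under standard care, because death before referral is a common competing event

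*Protocol*

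**What the plan says.** Section 19.1.2.1 of the Protocol sets the measure and its clock: "Time to specialist palliative care, defined as the time spent on standard of care will be measured from the date of registration to" two end dates, the referral to SPC and the first SPC visit. Section 19.1.3 fixes the estimator: "Time to specialist palliative care referral, and to first treatment will be reported via the method of Kaplan and Meier", summarised by a median with its 95% confidence interval. I take first treatment there to be the first SPC visit of 19.1.2.1. Neither section names a competing-risk method.

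Four other places bear on the point:

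- Section 2.2.1 gives the use: time to specialist palliation, with the treatments delivered, will "aid in defining the primary research question in the RCT".
- Section 19.2.5.1 gives the mortality: "Assuming a median survival time in these patients of six months and an exponential distribution". From this it expects 70% alive at three months.
- Section 3.2 counts early referral in weeks from diagnosis, and section 5.1 allows consent up to four weeks after the MDT confirms the diagnosis.
- Section 19.1.5 closes the feasibility study after a minimum of three months' follow-up. The visit schedule runs to six months.

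**The concern.** A patient who dies without referral can no longer be referred. Kaplan-Meier with that death censored treats the patient as still at risk, and spreads their share over those still alive. The curve then describes referral in a population where nobody dies. What the planners need is the proportion of standard-care patients who reach SPC, and when.

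The error has one direction: standard care appears to refer more patients, and sooner, than it does. The contrast between Arm A and Arm B depends on how late and how often standard care refers, so the size of that contrast would look smaller than it is.

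A lesser point concerns the clock. Registration may fall up to four weeks after diagnosis, which is the far end of the window that section 3.2 calls early. The eligibility criteria do not exclude patients already referred. Such patients have a zero or negative time on this clock, and a curve from registration alone does not show how many were referred early in the section 3.2 sense.

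**Working it through.** **Inputs from the Protocol.** Median survival is six months, exponential (19.2.5.1). The planned size is 60 patients (19.1.6), with minimum follow-up of three months (19.1.5).

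**Assumption.** The Protocol gives no referral rate under standard care. I take exponential referral, independent of death, with a median m from 1 to 12 months in the absence of death.

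**Step 1: reproduce the Protocol's figure.** With death hazard l = ln2/6, S(3) = exp(-3l) = 0.707 against the stated 70%. S(6) = 0.50. The 6.5-month median in section 1.1 would give S(6) = 0.527, about 47% dead.

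**Step 2: formulas.** Let g = ln2/m.

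- One minus Kaplan-Meier, deaths censored: 1 - exp(-g t).
- Proportion actually referred: CIF(t) = g/(g+l) × [1 - exp(-(g+l) t)].
- Time by which half are referred: -ln[1 - 0.5(g+l)/g]/(g+l), which exists only if g/(g+l) > 0.5.

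**Step 3: example, m = 3.** Here g/(g+l) = 2/3.

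- At six months: 1-KM = 1 - 2^(-2) = 75.0%; CIF = 2/3 × (1 - 2^(-3)) = 58.3%.
- At three months: 1-KM = 50.0%; CIF = 2/3 × (1 - 2^(-1.5)) = 43.1%.
- Half referred: Kaplan-Meier gives 3.0 months. The actual time is -ln(0.25)/(ln2/2) = 4.0 months.

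**Step 4: range.**

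| m (months) | 1-KM vs CIF at 3 months | Gap (points) | 1-KM vs CIF at 6 months | Gap (points) | Half actually referred by (months) |
|---|---|---|---|---|---|
| 1 | 87.5% vs 78.1% | 9.4 | 98.4% vs 85.0% | 13.4 | 1.08 |
| 2 | 64.6% vs 56.2% | 8.4 | 87.5% vs 70.3% | 17.2 | 2.38 |
| 3 | 50.0% vs 43.1% | 6.9 | 75.0% vs 58.3% | 16.7 | 4.0 |
| 4 | 40.5% vs 34.8% | 5.8 | 64.6% vs 49.4% | 15.3 | 6.2 |
| 6 | 29.3% vs 25.0% | 4.3 | 50.0% vs 37.5% | 12.5 | not reached |
| 12 | 15.9% vs 13.5% | 2.4 | 29.3% vs 21.5% | 7.7 | not reached |

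Gaps are taken before rounding. In this model the Kaplan-Meier median equals m. At m = 6 the hazards are equal and CIF only approaches 50%.

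**Step 5: simulation.** With 60 patients, six months of follow-up and 4,000 runs, 1-KM at six months averaged 75.1% against 58.2% actually referred (m = 3), and 50.0% against 37.4% (m = 6).

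**Step 6: the other coding of death.** If death counted as an event, the curve would be 1 - exp(-(g+l) t). For m = 3 that is 1 - 2^(-3) = 87.5% at six months, with median ln2/(g+l) = 2.0 months. This is time to referral or death, and it is further from the 58.3% and 4.0 months than the censored version.

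**Step 7: referrals before registration.** A lag of two weeks is 0.46 months and of four weeks 0.92 months. With a referral median from diagnosis of 1 to 6 months, 1 - exp(-g × lag) gives 5% to 27% already referred at a two-week lag and 10% to 47% at four weeks.

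**The case against.** **The output is only descriptive.** Section 19.1.3 rules out hypothesis testing, and the key progression targets in 19.1.1 concern willingness to be randomised and questionnaire completion. A reader might infer that the decision to proceed rests on this estimate; the Protocol does not say so. That limits the weight of the point. It does not make the estimator right, since section 2.2.1 gives the result a use in design.

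**Coding of death is normal SAP content.** True, and the SAP is not at hand. Time spent on standard of care could also be read as ending at death. But the Protocol itself fixes Kaplan-Meier with a median, and neither way of coding death within Kaplan-Meier yields the proportion referred.

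**The size is assumed, and smaller at three months.** Correct. With 60 patients and no censoring, a 95% interval near 43% is about ±12.5 points (1.96 × √(0.431 × 0.569/60) = 0.125), wider than the 7-point gap at three months. If the sickest patients are the ones referred, the unreferred die more slowly than assumed and the gap shrinks. The direction stands: with deaths censored, one minus Kaplan-Meier is never below the cumulative incidence.

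**The clock should move to diagnosis.** A reader might infer this from section 3.2. The Protocol does not support it. Arm B patients are referred immediately once randomised (7.2.1.2), and the three-month GHSS and overall survival run from randomisation (19.2.1). Registration therefore matches the clock on which the arms are compared. Starting at diagnosis without delayed entry would also credit survival that patients needed in order to be registered.

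**Site eligibility is affected.** Section 7 says: "Sites in which all patients are referred early, i.e. within two to four weeks, to SPC will not be eligible". A reader might infer that this estimate decides which sites qualify. The rule concerns site practice, nothing ties it to this analysis, and the estimate comes from the feasibility centres only.

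**Conclusion.** The point holds for the estimator. Kaplan-Meier with deaths censored will overstate how many standard-care patients reach SPC and understate the time by which half do. Under the Protocol's survival assumption and assumed independent exponential referral medians of 1 to 12 months, the overstatement is about 2 to 9 points at three months and 8 to 17 points at six. The direction needs no assumption about the referral rate; the size does.

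On the clock, only a limited point holds. Registration is a sound origin for the main estimate, but it does not by itself describe early referral as section 3.2 defines it, so a supplement from diagnosis is useful. The defect lies in a descriptive feasibility output. It leaves the randomised comparison and the listed progression criteria untouched, but it should be corrected before the estimate is used to shape the randomised trial.

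**What to change.** 1. In 19.1.3, replace Kaplan-Meier for this measure with the Aalen-Johansen cumulative incidence of SPC referral and, separately, of first SPC visit, with death before SPC as the competing event. Give the proportion referred at stated times with 95% confidence intervals, and the time by which half are referred only if the curve reaches 50%.
2. Keep registration as the time origin in 19.1.2.1.
3. Report the number and proportion already referred before registration.
4. Add, as a supplementary description, the time from MDT-confirmed diagnosis to referral, allowing for delayed entry at registration.

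The cost is small. Dates of death (7.1.3) and details of SPC referral at follow-up (7.1.1.2) are already collected. The diagnosis date is not among the items listed at registration (6.1) and must be recorded, and the baseline list (7.1.1.1) does not name an existing SPC referral, so that date needs a place on the form. The analysis work increases slightly. With about 20 patients per centre, any site-level results are best kept to simple proportions.

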19.1.4 Planned Sub-group Analyses

Where appropriate outcome measures will be analysed by mGPS and ECOG performance score, accordingly.

19.1.5 Planned Final Analyses

The feasibility study will be closed once all patients have been followed for a minimum of three months. The data will be reported to the TSC and the feasibility of proceeding to the RCT shall be assessed.

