3.1 Feasibility Study

The first stage is a six month feasibility study in which key elements of the later randomised trial will be tested for relevance, acceptability and viability. There is no intervention in the feasibility study.

At three cancer centres, consecutive, newly diagnosed, stage IV NSCLC patients will be identified at weekly Lung Cancer multi-disciplinary team (MDT) meetings. Eligible patients will be approached to enter the feasibility study at the next clinic visit.

Patients will be reviewed in clinic every month (or alternatively every third week while receiving three-weekly treatment) for six months. Please note the timing of assessments while patients are undergoing treatment will coincide with clinic visits for example: chemotherapy three-weekly; targeted therapy four-weekly; radiotherapy four weekly.

Hospital records will also be checked weekly during the feasibility study recruitment phase to identify any patients coded with a diagnosis of lung cancer but who were not discussed at the Lung Cancer MDT meeting. Recruitment will either continue at each centre until at least 20 patients have entered the study or for a period of three months from opening to recruitment at each site.

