7.1.1.2 Follow-up Assessments

The patient should be followed-up at least once per month for six months. Patients being treated every third week (for example those receiving chemotherapy) will be seen every three weeks while on treatment. The patient's visits should be organised to correspond with their treatment visits where possible.

The following should be assessed at each visit (be that three weekly of four weekly):

- Disease status
- ECOG status (see Appendix 6)
- Concomitant medication

The patient should be asked to complete the following during the clinic appointment:

- Appropriate Follow-up Patient Questionnaire Booklet
- SPARC (see Appendix 2)

In addition to the above, at the **three and six month assessments**, the following must also be assessed:

- mGPS (see Appendix 3 and Section 7.3)
- MoCA (see Appendix 4) only for those patients who consent to this optional measure of cognitive function

The patient should be asked to complete the Patient Feedback Questionnaire at their 3 month followup assessment

The carer should be asked to complete the Carer Questionnaire Booklet. If the trial registered carer is not accompanying the patient, please send the carer questionnaire booklet home with patient so that the carer may complete and return it to the site research team at the next follow-up clinic visit.

Completed questionnaire booklets and forms should be returned to the Trial Office with the patient's completed diary sheets.

Please note: The patient may require a new Patient Diary after their six month assessment visit.

A larger format version of the diary is available (A4, larger font size) for patients who require large print.

The following information will be collected on the CRF at all follow-up visits:

- Disease status
- ECOG status (see Appendix 6)
- Concomitant medication
- Treatment details
- Response to treatment (determined as per local practice)
- Hospital admissions, including duration and reason for admission
- Details of relapse/progression
- Details of patient referral to the SPC team
- Resource use (see Appendix 1 for list of medical interventions)

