19.1.6 Sample Size Justification

The feasibility study aims to register 60 patients over a three-month period. There is no statistical basis for this sample size; 60 was chosen as a logistically sensible number deemed sufficient to inform the RCT.

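### The feasibility study closes at three months' minimum follow-up, too early for its six-month EQ-5D-5L progression criterion and early enough to weaken its six-month survival check

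*Protocol*

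**What the plan says.** Section 19.1.5 sets the closing time: "The feasibility study will be closed once all patients have been followed for a minimum of three months". It continues: "The data will be reported to the TSC and the feasibility of proceeding to the RCT shall be assessed". So closure, reporting and the progression assessment are tied to the same point.

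Other parts of the protocol ask for six-month information:

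- Section 19.1.1 includes among the progression targets "Completion of EQ-5D-5L at the six month end point (80% of surviving patients").
- Section 19.1.3 says of overall survival: "The six-month survival rate (95% CI) will be reported and the validity of the power calculation for the RCT will be assessed".
- Section 7.1.1.2 schedules visits to match: "The patient should be followed-up at least once per month for six months". Table 1 agrees.

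The timeline comes from two places. Section 19.1.6 says "The feasibility study aims to register 60 patients over a three-month period". Section 3.1 says "The first stage is a six month feasibility study in which key elements of the later randomised trial will be tested", and on accrual: "Recruitment will either continue at each centre until at least 20 patients have entered the study or for a period of three months", counted from each site's own opening.

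**The concern.** Three months of accrual plus three months of minimum follow-up makes exactly the six-month stage described in 3.1. On that timeline follow-up at closure runs from three months (last patient in) to six months (first patient in), so the six-month visit falls at or after the closing date for essentially everyone.

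Quality-adjusted survival over six months is a co-primary outcome of the RCT. It is built from repeated EQ-5D-5L utilities, with imputation where they are missing. The six-month completion target is the only numeric progression criterion on EQ-5D-5L; the other two numeric targets concern GHSS, at baseline and at three months. If it cannot be judged when the decision is taken, late attrition on that co-primary goes untested. The survival check has a milder form of the same problem.

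**Working it through.** **Inputs**

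- 60 patients over three months (19.1.6); closure when the last patient has three months of follow-up (19.1.5).
- Exponential survival with a median of six months (19.2.5.1, stated for the RCT): S(t) = 0.5^(t/6).
- Assumption: entry is uniform over the accrual period.
- Assumption: a six-month visit up to two weeks early counts. The protocol gives a two-week window only for the RCT's three-month GHSS (19.2.2.1). Two weeks = 14/30.44 = 0.46 months.

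**Reproducing the plan's figures.** Three centres × 20 = 60 patients. S(3) = 0.5^(3/6) = 0.707, which matches the stated 70% alive at three months. S(6) = 0.50.

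**Survivors who could supply a six-month EQ-5D-5L at closure, on the stated timeline**

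- No window: 0.
- One-week window (0.23 months): 60 × 0.23/3 = 4.6 patients reach it, and about 2.3 are alive.
- Two-week window: 60 × 0.46/3 = 9.2 patients reach 5.54 months. Between 9.2 × 0.50 = 4.6 and 9.2 × 0.5^(5.54/6) = 4.9 are alive, so about 5. A median of 6.5 months gives 4.9 to 5.1.
- Every patient followed to six months: 60 × 0.50 = 30.

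**What that means for an 80% target (exact 95% CI).** 4/5: 28% to 99%. 24/30: 61% to 92%.

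**If overall accrual takes a months and closure is at a + 3.** Without a window the count is 60 × (a − 3)/a × 0.50. With two weeks it is 60 × (a − 3 + 0.46)/a × 0.5^(5.54/6).

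| Accrual (months) | Survivors at a full six months | With two-week window |
|---|---|---|
| 3 | 0 | 4.9 |
| 4 | 7.5 | 11.5 |
| 5 | 12 | 15.6 |
| 6 | 15 | 18.2 |

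At 15 survivors, 12/15 has an exact 95% CI of about 52% to 96%.

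**Six-month survival.** With follow-up uniform on three to six months, the mean probability of being alive at closure is (0.7071 − 0.5)/(3 × ln 2/6) = 0.598. About 60 × 0.402 = 24 deaths are therefore observed. A simulation of the Kaplan-Meier estimate (2,000 runs, n = 60, this censoring) gave:

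- about 5 at risk at 5.5 months, 2.6 at 5.75, 0.5 at 5.95 and 0 at 6;
- a standard deviation of 0.109 at 5.95 months and 0.116 at 6 months. Since 0.25/SD² is about 21 and 18.5, this is the precision of roughly 18 to 21 fully followed patients.

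With full follow-up the standard error is √(0.25/60) = 0.064. The 95% half-width is thus about 0.21 to 0.23 at closure, against 0.13 with full follow-up.

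**The case against.** **The criteria are not a hard gate.** Section 19.1.1 says the targets guide the decision, with discretion and a view of the whole. Section 19.1 proposes no formal stopping guidelines and puts the focus on recruitment. This stands and limits the consequence. But discretion over how to weigh a criterion does not supply its data.

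**Earlier EQ-5D-5L data exist.** The instrument is in every booklet (Table 3), and 19.1.3 reports return and missingness by visit. The committees would see completion up to closure, which informs an area-under-the-curve outcome. This also stands, but it says little about the last months of the curve.

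**The timeline may be longer.** The closing rule is a minimum, and 3.1 counts three months from each site's opening, so staggered opening would raise the counts. This stands; a reader might take 0 to 5 as a fixed count, and it is not. Even with six months of accrual, however, the number at a full six months is half of 30, and it gets there only by missing the accrual plan in 19.1.6.

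**Section 19.2.4 may imply waiting.** It refers to completion of the feasibility study and receipt of all data, but gives no six-month point for that stage, whereas it does tie the RCT analysis to the six-month visit.

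**Two stronger readings fail.** A reader might infer that the survival check also rests on 0 to 5 patients. It does not: that is only the number at risk near six months, and Kaplan-Meier uses all 60 patients and about 24 deaths. A reader might also infer that six-month survival is the wrong quantity to check because the GHSS calculation uses three-month survival. Section 19.2.5.1 derives its 70% from an assumed six-month median, which six-month survival tests directly.

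**Conclusion.** The closing rule in 19.1.5 contradicts the six-month EQ-5D-5L criterion in 19.1.1, and nothing elsewhere in the protocol makes the decision wait. Under uniform entry in one common three-month period and the plan's survival model, between 0 (no window) and about 5 (two-week window) survivors could inform the criterion, against about 30. If accrual stretches to 4 to 6 months the figure is about 7 to 15 without a window. On the stated timeline the result could not separate success from failure against 80%.

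For survival the conclusion is weaker: the six-month rate can be produced, but at the edge of follow-up and with nearly twice the standard error. The progression decision as a whole is not undermined, because the other listed criteria can be assessed by three months and all are applied with discretion.

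**What to change.** Amend 19.1.5 so that the six-month EQ-5D-5L criterion and six-month survival are assessed when every patient has reached six months or died. Section 7.1.1.2 and Table 1 already schedule those visits. The cost is a decision about three months later, and the description of a six-month stage in 3.1 would need to change with it.

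If the decision date cannot move:

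- base the go/no-go in 19.1.1 on EQ-5D-5L completion at visits up to three months;
- check the assumed survival at three months against the 70% in 19.2.5.1;
- report six-month completion and survival to the DMC before the RCT sample size is finalised.

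This keeps the date but has a price. Late attrition is not judged at the go/no-go. A three-month EQ-5D-5L target also largely overlaps the existing three-month GHSS criterion, since both instruments sit in the same booklet (Appendix 8). The protocol should then say plainly that the six-month items are not part of the progression decision.
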